6.4.2 Replacement

Subjects will not be replaced.

6.5 Subject identification

The subject number is a 9-digit number consisting of:

Digits 1 to 5 = Unique center number

Digits 6 to 9 = Current subject number within the center

7. Device

7.1 Device used

- The FDA approved Essure System (ESS305).
- Approved medical devices used for laparoscopic tubal sterilization such as cautery devices, clips, rings, etc.

7.2 Choice of Procedure

The decision to participate in the post-marketing surveillance study must be independent of the subject's decision to undergo a permanent sterilization procedure and of the type of sterilization procedure selected. This is a non-randomized, continuous enrollment study in which all eligible subjects who desire permanent contraception (female sterilization) via bilateral occlusion of the fallopian tubes with the approved Essure device or laparoscopic tubal sterilization procedure will be asked to enroll.

Part of the counseling process for Essure includes providing the PIB and a patient checklist. Receipt of the PIB and completion of the patient checklist will be part of the inclusion criteria for the Essure group. A similar process will be carried out after signing the informed consent

and prior to performance of the laparoscopic tubal sterilization procedure. These subjects will be provided with a copy of the ACOG brochure on laparoscopic tubal sterilization procedures. In addition, they will receive a patient checklist that is modeled on the final format of the patient checklist that is part of the labeling for Essure.

7.3 Blinding

Not applicable.

7.4 Device logistics and accountability

7.4.1 Device placement compliance

Subjects in the Essure group are required to use alternative contraception until they are told to rely on Essure for contraception (after an Essure Confirmation Test). The Essure device is intended for subjects who desire permanent contraception (female sterilization) and is not intended to be removed.

Subjects who are not told to rely on Essure, regardless of whether or not they have an insert in situ, will continue to be followed in the study for safety data.

8. Non-study therapy

8.1 Prior and concomitant therapy

Information will be collected on the method(s) of contraception each subject has used and the duration of use in the period immediately prior to participation in this study (prior to undergoing permanent sterilization). Data will also be collected on the method of alternative contraception used by Essure subjects during the period in which they are unable to rely on Essure. All concomitant medications used during the study and prior medications used up to 2 years prior to study participation will be collected and entered into the CRF.

Special attention will be given to the following:

- Each woman's history of use of medication to treat heavy menstrual bleeding or pelvic or abdominal pain;
- Pain medication used or prescribed for the initial sterilization procedures;
- Pain medication used or prescribed for AEs of pain during study participation;
- Use of medication or other treatments to treat AEs of bleeding during study participation;
- Use of any additional contraceptive medications or methods during participation in the study;
- Use of medications to treat any suspected allergic / hypersensitivity reactions;
- Use of medications to treat any suspected immunological disorders.

8.2 Post-study therapy

After the end of this study, further treatment is not necessary since only healthy subjects will be included in the study.

9. Procedures and variables

9.1 Tabular schedule of evaluations – amended

Section modified by Amendment 1 (Section 16.1), Amendment 2 (Modification 3, Modification 4, Modification 5, Modification 13, Modification 14, Modification 16, Modification 17, Modification 20), and Amendment 3 (Modification 2).

Table 9–1 shows the schedule of evaluations for the procedures for the study. Table 9–2 shows the schedule for the PRO procedures.

Due to local regulations impacting the study center due to COVID-19, it is possible that not all planned assessments could be performed or if they had been included in the eCRF, they could not all be verified. The protocol deviations related to COVID-19 will be identified in the by-subject listings.

[illegible]

Integrated Clinical Study Protocol
BAY 1454032 / 18894

28 JUN 2022

Version 5.0

Page: 32 of 149

Schedule of evaluations	Screening	Procedure (1 st or 2 nd)	Post procedure (before discharge)	1 week post procedure (contact)	3 months post procedure (± 2 wk) ^a	12 months (± 4 wk)	24 months (± 4 wk)	36 months (± 4 wk)	48 months (contact; ± 4 wk)	60 months (end of study) (-4 wk, +1 wk)	Premature Discontinuation (Dropout)
Concomitant procedures		•									
Assessment of ability to access tubes (easy, moderate, difficult)		•									
Assessment of procedural difficulty		•									
Conversion to laparotomy if needed –data associated with laparotomy		•									
Location of procedure (type of facility)		•									
ESSURE SYSTEM PROCEDURAL CHARACTERISTICS:											
Type of anesthesia, location of procedure		•									
Length of procedure and time in recovery		•									
Physician assessment of procedural difficulty		•									
Reasons for procedural difficulty or complications		•									
Number of attempts at placement		•									
Concomitant procedures		•									
Post-placement insert location, number of trailing coils		•									
Unique Device Identifier		•									
Second attempt if necessary (need to collect all data)		•									
Confirmation test modality (or reason for non-compliance)					• ^h						
Confirmation test results, repeat if necessary					• ^h						
SURGICAL PROCEDURES INCLUDING DEVICE REMOVAL:											
Procedure / method of device removal			→	→	→	→	→	→	→	→	
Complications and outcomes of surgical procedure / device removal (e.g., symptom resolution)			→	→	→	→	→	→	→	→	
Pathology and metallurgic studies			→	→	→	→	→	→	→	→	
INTRA-OPERATIVE AND POST-PROCEDURE:											
Infection, uterine or tubal perforation, device migration, device expulsion, port site hematoma / bleeding			→	→	→	→	→	→	→	→	
Pregnancy including pregnancy outcomes			→	→	→	→	→	→	→	→	•
In cases of potential hypersensitivity / allergy / autoimmune reactions ^{f,i} / pain AEs, whole blood and serum for laboratory testing including NiLPT, chromium LPT, serum or plasma nickel, serum titanium, HLA panel (autoimmune disease only), and inflammatory cytokines			→ ^j	→	→	→	→	→	→	→	

Integrated Clinical Study Protocol

BAY 1454032 / 18894

28 JUN 2022

Version 5.0

Page: 33 of 149

ACOG=American College of Obstetrics and Gynecology, AE=adverse event, AUB=abnormal uterine bleeding, HLA=human leukocyte antigen, HLA-DR = HLA-antigen D Related, LTS = laparoscopic tubal sterilization, NiLPT=nickel lymphocyte proliferation test, wk=week(s).

→ To be done when needed, starting from the time point indicated.

- ^a For the Essure group, the 3-month contact window is + 2 weeks, and the results of the confirmation test should be available at the time of the contact.
- ^b Final check of inclusion / exclusion criteria should be conducted during the study procedure period.
- ^c The physical examination only needs to be performed once, unless the subject history has changed. If not performed prior to the Screening, the physical examination should be performed within 6 weeks prior to the procedure. The results of pelvic examinations performed within the 6 weeks prior to screening can be used unless the subject history has changed.
- ^d Height is only measured once, at screening (or at the procedure visit, if it was not already measured at screening).
- ^e To characterize nickel hypersensitivity, an HLA panel (HLA-DR subunits B1, B3, B4, and B5) will be performed for all subjects using the baseline sample. To characterize specific autoimmune diseases in subjects with an autoimmune disease diagnosis, an HLA panel will be performed, using any remaining sample. The HLA type to be evaluated will be selected in consultation with an immunologist and / or rheumatologist and will depend on the specific autoimmune disease diagnosed. The HLA panel will be run on the index case as well as a randomly selected control group. If insufficient baseline sample exists, an additional sample may need to be drawn.
- ^f Gadolinium and iodine-based contrast material are known to interfere with trace metal analysis. Specimen collection for serum/plasma nickel and titanium should be deferred until 96 hours following administration of gadolinium or iodine contrast media.
- ^g An inflammatory cytokines panel will be evaluated at baseline, 12 months, and 60 months. The assay will include IFN- γ , IL-10, IL-4, TGF- β , TNF- α , p40 subunit (IL-12, IL-23), p35 subunit (IL-12, IL-35), and IL-17. The assay will use frozen serum sample collected at baseline and 12 months. A new serum sample will be drawn at 60 months for cytokine analysis. Any leftover baseline and 12-month sample will be stored frozen for future use in subjects with diagnosed autoimmune disease. The 60-month sample will not be frozen.
- ^h The visit window for the 3-month contact does not apply to the confirmation test. The confirmation test should be conducted at 3 months post-procedure; however, the exact timing of this test is at the discretion of the investigator.
- ⁱ In cases of suspected autoimmune disorder, additional lab work will be analyzed, as indicated, on previously frozen serum samples (if sufficient sample is available). Any remaining serum sample will remain frozen.
- ^j Whole blood and serum or plasma for cases of hypersensitivity, autoimmune reactions, and pain AEs does not need to be taken before discharge; however, whole blood and serum or plasma sampling should occur if symptoms are indicated between discharge and the Week 1 contact.

Integrated Clinical Study Protocol
BAY 1454032 / 18894

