- Levels of inflammatory markers and HLA type in subjects with Essure and adjudicated hypersensitivity reactions can be compared to corresponding findings in subjects with Essure without hypersensitivity reactions as well as to laboratory results in laparoscopic tubal ligation subjects (with and without adjudicated hypersensitivity reactions). Serum cytokine values will be classified as below the normal range, within the normal range, or above the normal range, as appropriate. These values will be used to provide descriptive summaries of change of categories between baseline and

Year 1 and between baseline and Year 5. For these analyses the safety population will be used to present data by treatment groups and by symptomatic/asymptomatic subjects. Secondary analyses can also be performed in subjects who report positively to events on the Supplementary PRO tools (e.g. fatigue, headache) versus those who do not. These comparisons will not rely on device removal.

- Serum or plasma nickel and titanium levels in subjects with Essure and adjudicated hypersensitivity reactions can be compared to serum or plasma nickel and titanium levels in subjects with Essure without hypersensitivity reactions as well as to serum or plasma nickel and titanium levels in laparoscopic tubal ligation subjects (with and without adjudicated hypersensitivity reactions). Secondary analyses can also be performed in subjects who report positively to events on the Supplementary PRO tools (e.g. fatigue, headache) versus those who do not. These comparisons will not rely on device removal.
- NiLPT and chromium LPT results (both the continuous measurement as well as the positive / negative assessment) in subjects with Essure and adjudicated hypersensitivity reactions can be compared to NiLPT and chromium LPT results in subjects with Essure without hypersensitivity reactions as well as to NiLPT and chromium LPT results in laparoscopic tubal ligation subjects (with and without adjudicated hypersensitivity reactions). Secondary analyses can also be performed in subjects who report positively to events on the Supplementary PRO tools (e.g. fatigue, headache) versus those who do not. These comparisons will not rely on device removal.
- An individual subject's serum or plasma nickel and titanium levels and NiLPT can be compared to baseline levels in order to assess any change. In addition, in cases of removal, subsequent post-removal levels can also be compared.

Autoimmune diseases

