The LPT is a measure of sensitization to chromium. This test requires whole blood and must be received in the laboratory within 24 hours. Due to the very low positivity rate for this test, it will only be drawn if a subject develops symptoms that could be due to hypersensitivity or autoimmune process, including pelvic pain.
- Serum nickel level
This test will be drawn and run at baseline, at 12 months, and at 60 months in all subjects. In addition, if at any point in the study a subject develops symptoms that could be due to hypersensitivity or autoimmune process, including pelvic pain, an unscheduled serum nickel level will be re-drawn. Gadolinium and iodine-based contrast material are known to interfere with trace metal analysis; therefore, specimen collection for serum/plasma nickel and titanium should be deferred until 96 hours following administration of gadolinium or iodine contrast media.
- Serum titanium level
This test will be drawn and run at baseline and at 1 year in all subjects. In addition, if at any point in the study a subject develops symptoms that could be due to hypersensitivity or autoimmune process, including pelvic pain; an unscheduled serum titanium level will be re-drawn. Gadolinium and iodine-based contrast material are

known to interfere with trace metal analysis; therefore, specimen collection for serum/plasma nickel and titanium should be deferred until 96 hours following administration of gadolinium or iodine contrast media.

- Serum

Serum will be collected at baseline and at 1 year on all subjects. This serum will be frozen. For all subjects, this serum will be used to run a baseline and one-year inflammatory cytokine panel (to include IFN- γ , IL-10, IL-4, TGF- β , TNF- α , p40 subunit (IL-12, IL-23), p35 subunit (IL-12, IL35), and IL-17). Any remaining serum will be frozen. It will be used if a subject develops an autoimmune disease. In these cases, the serum can be used to obtain baseline levels for the particular diagnosed autoimmune condition (e.g. a Rheumatoid Factor if subject is diagnosed with rheumatoid arthritis; thyroid peroxidase antibody if subject is diagnosed with autoimmune thyroid disease. Given the number of potential diseases, it is not possible to establish a baseline for every potential autoimmune disease). If any serum remains after running these tests, it will remain frozen.

At 60 months, additional serum will be drawn. This will be sent for a repeat inflammatory cytokine panel.

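### The planned baseline-to-Year-5 cytokine shift sets frozen serum against unfrozen serum, so within each arm a freezing effect cannot be told apart from change since the procedure

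*Protocol*

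**What the plan says.** Footnote g to Table 9-1 (Protocol Section 9.1) sets three time points: "An inflammatory cytokines panel will be evaluated at baseline, 12 months, and 60 months". For the first two it says "The assay will use frozen serum sample collected at baseline and 12 months". For the third it says "A new serum sample will be drawn at 60 months for cytokine analysis", and later "The 60-month sample will not be frozen". Between these last two statements stands one about storage: "Any leftover baseline and 12-month sample will be stored frozen for future use in subjects with diagnosed autoimmune disease".

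The other sections follow the same pattern. Protocol Section 9.6.3.1 says of the first two draws "Serum will be collected at baseline and at 1 year on all subjects. This serum will be frozen", and of the last "At 60 months, additional serum will be drawn. This will be sent for a repeat inflammatory cytokine panel", with no freezing step. The 12-month visit text (9.2.2.7) asks for serum to be frozen. The 60-month visit text (9.2.2.11) asks only for serum for the panel.

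For the analysis, Protocol Section 9.6.1.1 classifies each cytokine against its normal range. It then summarises change of category between baseline and "Year 1 and between baseline and Year 5", by treatment group and by symptomatic status. SAP Section 6.4 adds change from baseline at every post-baseline visit for each laboratory parameter.

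**The concern.** A within-woman shift can be read as biological change only if both measurements were obtained in the same way. Here the state of the sample changes at exactly the point where the long-term comparison is made. Every baseline value is from frozen serum and every 60-month value, as written, is from unfrozen serum, so no analysis of these data can separate handling from time.

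The 60-month panel is the only scheduled Year-5 cytokine result in all subjects. If freezing changes the reading, the shift tables could show a late inflammatory rise in both arms that did not happen, or hide one that did. Tables by symptomatic status within an arm have the same weakness. Neither document provides a stability or bridging check, a same-batch rule, a reference range specific to the handling, or a caveat on the Year-5 shift.

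**Working it through.** **Handling by time point, from the current text**

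| Time point | Sample state | Source |
|---|---|---|
| Baseline | frozen | footnote g; 9.2.1; 9.6.3.1 |
| 12 months | frozen | footnote g; 9.2.2.7; 9.6.3.1 |
| 60 months | not frozen | footnote g; no freezing step in 9.2.2.11 or 9.6.3.1 |

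Baseline to Year 1 is frozen against frozen. Baseline to Year 5 is frozen against unfrozen.

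**Illustration of size.** The plan gives no cytokine variance, freezing effect or expected shift, so there is no figure of its own to reproduce. Every input here is an assumption:
- lognormal marker, with between-person log-SD s = 0.4 or 0.6 and within-person log-SD 0.2
- freezing multiplies the reading by f = 0.9, 0.8 or 0.7
- normal limits at the 2.5th and 97.5th percentiles of unfrozen serum
- no true change over time.

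Formulas:
- total log-SD T = √(s² + 0.2²), which is 0.447 or 0.632
- within-woman correlation ρ = s²/T², which is 0.80 or 0.90
- offset in SD units d = −ln(f)/T
- share above normal at baseline = 1 − Φ(1.96 + d)
- share above normal at Year 5 = 2.5% by construction
- shares moving up or down a category from the bivariate normal distribution with correlation ρ.

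Example: f = 0.7 and s = 0.4 give d = 0.357/0.447 = 0.798, and 1 − Φ(2.758) = 0.29%.

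| Loss | s | d | Above normal at baseline | Shift up | Shift down | Up : down |
|---|---|---|---|---|---|---|
| 10% | 0.4 | 0.236 | 1.41% | 4.52% | 1.69% | 2.7 |
| 10% | 0.6 | 0.167 | 1.67% | 3.20% | 1.22% | 2.6 |
| 20% | 0.4 | 0.499 | 0.70% | 7.42% | 0.91% | 8.1 |
| 20% | 0.6 | 0.353 | 1.04% | 5.01% | 0.64% | 7.8 |
| 30% | 0.4 | 0.798 | 0.29% | 12.38% | 0.414% | 29.9 |
| 30% | 0.6 | 0.564 | 0.58% | 7.83% | 0.275% | 28.4 |

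Shifts are counted on the plan's three-category scale. Counting only crossings of the upper limit, the ratio at 30% loss is 34.9 (s = 0.4) or 29.9 (s = 0.6). The large ratios owe much to a small denominator: about 0.07% of women move down across the upper limit and 2.0-2.3% move up.

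**Different reference basis.** If the limits instead fit the baseline (frozen) distribution and month 60 is offset upward by 0, 0.25, 0.5 or 1.0 SD, the share above normal at month 60 is 1 − Φ(1.96 − d) = 2.5%, 4.4%, 7.2% or 16.9%. With a within-woman correlation of 0.7, upward against downward shifts are about 3.3% each way with no offset, then 5.1% v 2.1%, 7.9% v 1.4% and 17.2% v 0.5%. An offset in the other direction gives the mirror image.

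**The case against.** The strongest objection is to the reading of the sentence. It follows directly after the one on leftover serum, so it may mean only that no 60-month serum is banked. Section 9.6.3.1 has a similar order, and detailed handling is left to a lab manual that is not among the documents. This reading is possible, but it is not the literal text: the sentence speaks of the sample, not the remainder, and no 60-month instruction includes freezing. Under either reading the footnote needs rewording, because a site that followed it literally would not freeze.

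The second objection is that little depends on this result. The summaries are descriptive, cytokines are not among the main endpoints in SAP Table 2, and no confirmatory test is planned. Both arms are handled alike at each visit, so the laparoscopic arm acts as a concurrent control for a common offset. This stands and limits the point to interpretation. The protection is not exact on a three-category scale if the arms sit at different distances from the limits.

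Four stronger readings are tempting, and the documents do not support them:
- **Freezing is known to distort these cytokines.** Nothing in either document gives a size or direction, and the effect may be near zero for some of them.
- **Unfrozen 60-month serum cannot be run together with stored aliquots.** It could be assayed beside a thawed aliquot. No batch arrangement is stated for any time point.
- **The Year-1 shift is free of handling effects.** It is matched on freezing only. Storage time and assay run are not specified, and Protocol Section 16.2.1 (Modification 4) shows that serum was already being stored before the panel was added.
- **The comparison of Essure with laparoscopic sterilization is invalid.** Identical handling in both arms largely protects the difference in shift.

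**Conclusion.** The point holds for the within-arm shift. On the current wording, sample state is fully aliased with time point in the baseline-to-Year-5 category change, and no provision addresses it. This follows from the text alone and does not depend on the illustration.

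The practical size is unknown. Under the assumed 10-30% loss, with no true change, 0.3-1.7% of women are above normal at baseline against 2.5% at Year 5. Upward shifts outnumber downward ones by about 2.6 to 1 at the low end and about 28-30 to 1 at the high end. These figures depend on the assumed direction, spread and reference limits. With no freezing effect, the imbalance disappears.

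The consequence is limited to interpreting a descriptive secondary result. It still deserves correction, because the remedy is simple and the result is the only scheduled long-term cytokine measure in all subjects.

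**What to change.** 1. Amend footnote g and Protocol Section 9.6.3.1 so that 60-month serum still to be drawn is frozen and handled before assay as at baseline and 12 months. If the sentence was meant only to say that no 60-month serum is banked, reword it to say so, and align the 60-month visit text and the lab manual.
2. For samples already run unfrozen, do not interpret the within-arm Year-5 shift as biological change. Present it separately with that caveat, and rely on the between-arm contrast of the shift and on the frozen-to-frozen Year-1 shift. Keep the contrast of shifts rather than replacing it with a 60-month comparison alone: in a non-randomised study it retains each woman's baseline.
3. Do not require leftover baseline aliquots to be re-run. Footnote g reserves them for women with diagnosed autoimmune disease, and a leftover aliquot may have had an extra thaw and would have been stored for years longer.

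The cost is a small lab-manual change, using frozen handling that the protocol already specifies at two visits, and a less interpretable Year-5 shift for women already assayed. The documents do not say how many 60-month samples remained to be drawn at protocol version 5.0.

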28 JUN 2022

Version 5.0

Page: 34 of 149

Table 9–2 Schedule of PRO evaluations

Questionnaire	Baseline	Week 1 [§]	Week 2 [§]	Week 3 [§]	Week 4 [§]	Month 2**	Month 3 [‡]	Month 6 [‡]	Month 9 [‡]	Month 12 [‡]	Month 15 [‡]	Month 18 [‡]	Month 21 [‡]	Month 24 [‡]	Month 27 [‡]	Month 30 [‡]	Month 33 [‡]	Month 36 [‡]	Month 48	Month 60	Premature Discontinuation (Dropout)
PROMIS Scale v1.0 – Pain Intensity 3a ^{*†}	•	•	•	•	•	•	•	•	•	•	•	•	•	•	•	•	•	•	•	•	
PROMIS Scale v1.0 – Pain Interference 8a Participant Format ^{*†}	•	•	•	•	•	•	•	•	•	•	•	•	•	•	•	•	•	•	•	•	
Aberdeen Menorrhagia Severity Scale; and two intermenstrual bleeding questions	•						•	•	•	•	•	•	•	•	•	•	•	•	•	•	
SF-36	•							•		•				•				•		•	
Fibromyalgia Survey Questionnaire	•																				
Supplemental PRO Questionnaires										•				•				•	•	• ^{§§}	
Social Media Questionnaire																			• ^{§§}	•	

PRO=patient reported outcome, PROMIS=patient reported outcome measurement information system, SF-36=Short Form-36.

*All subjects are asked screening question “Did you experience pain in your pelvic area or in your lower abdomen during the past week?” Subjects that answer “Yes” complete both the PROMIS Scale v1.0 – Pain Intensity 3a and PROMIS Scale v1.0 – Pain Interference 8a Participant Format. Subjects that answer “No” do not have to complete the questionnaires.

[†] In the event a subject spontaneously reports an adverse event of pain, the subject will be given both the PROMIS Scale v1.0 – Pain Intensity 3a and PROMIS Scale v1.0 – Pain Interference 8a Participant Format questionnaires to complete at the time of reporting.

[§] Subjects completing ePRO questionnaires will receive email or text reminders to complete questionnaires 2 days prior to the scheduled completion date. The window for completion will be -2 days / +2 days for all questionnaires. If the questionnaire(s) are not completed by the scheduled completion date, another reminder will be sent and an alert will be sent to the site. Subjects completing paper questionnaires will not receive automated reminders and every effort will be made to ensure the subject completes the questionnaire within the window.

** Subjects completing ePRO questionnaires will receive email or text reminders to complete questionnaires 5 days prior to the scheduled completion date. The window for completion will be -5 days / +5 days for all questionnaires. If the questionnaire(s) are not completed by the scheduled completion date, another reminder will be sent and an alert will be sent to the site. Subjects completing paper questionnaires will not receive automated reminders and every effort will be made to ensure the subject completes the questionnaire within the window.

[‡] Subjects completing ePRO questionnaires will receive email or text reminders to complete questionnaires 1 week prior to the scheduled completion date. The window for completion will be -1 week / +2 weeks for all questionnaires. If the questionnaire(s) are not completed by the scheduled completion date, another reminder will be sent and an alert will be sent to the site. The subject and site will then receive weekly reminders and alerts at +1 week and +2 weeks. Subjects completing paper questionnaires will not receive automated reminders and every effort will be made to ensure the subject completes the questionnaire within the window.

^{§§} Subjects will complete Supplemental PRO Questionnaires at 12, 24, 36, 48, and 60 months. Subjects will complete a Social Media Questionnaire at 60 months (or Premature Discontinuation visit if applicable).

